1. PURPOSE OF STUDY

We hypothesize that daily intake of sulforaphane (Avmacol Extra Strength (ES)) can decrease kidney disease progression rate and decrease markers of oxidative stress and inflammation in chronic kidney disease (CKD) patients. We will test our hypothesis in a randomized, double-blind, placebo-controlled Phase 1/2 clinical trial in a single center, two sites, 3-year study. This proposed study was submitted as an R01 application in response to FOA PAS-20-160 that encourages submission of pilot and feasibility clinical trials that will lay the foundation for larger clinical trials related to the prevention/treatment of CKD within the mission of NIDDK. We have received a Notice of Award for this study from NIH/NIDDK.

There are two phases to our study; each will have a separate Consent Form. This proposal is only for Phase I study. Once Phase I is complete, a new study will be submitted for Phase II. Please see study design below for details:

1. Phase I: Establish pharmacokinetics of Avmacol ES in patients with CKD Stages 3-4 (first 6 months of the study). Subjects who participate in the first phase of the study may be eligible to participate in the second phase of the study.

We seek approval for the Phase I of the study which will establish the dosing for the second phase of the study.

2. BACKGROUND AND RATIONALE

In the United States (U.S.), the prevalence of chronic kidney disease (CKD) in adults is \sim 14%. The mainstay of therapy for CKD are angiotensin-converting enzyme inhibitors (ACE-Is) or angiotensin receptor blockers (ARBs), but many CKD patients still progress to end stage kidney disease (ESKD) – the ultimate in failed prevention. The prevalence of ESKD is \sim 700,000, and is projected to increase to between 971,000 – 1,259,000 patients by 2030 1 .

Increased oxidative stress is a major molecular underpinning of CKD progression. In humans, a common deletion variant of the glutathione-S-transferase μ-1 (*GSTM1*) gene, the *GSTM1* null allele (*GSTM1(0)*), results in decreased GSTM1 enzymatic activity and is associated with higher levels of oxidative stress. GSTM1 belongs to the superfamily of GSTs that are phase II antioxidant enzymes and are regulated by nuclear factor erythroid 2-related factor 2 (Nrf2). Our laboratory made the discovery that the highly prevalent *GSTM1(0)* is associated with more rapid CKD progression in the African American Study of Kidney Disease (AASK) trial participants ². This association has been replicated in the Atherosclerosis Risk in Communities (ARIC) study ³. In experimental mouse models of CKD or hypertension, we found *Gstm1* knockout (KO) mice have increased renal oxidative stress, inflammation, and kidney injury, compared to wild-type (WT) littermate controls ⁴.

Cruciferous vegetables in general, and broccoli in particular, are rich in glucoraphanin, a precursor of sulforaphane (SFN) that has been shown to have protective effects against oxidative damage through activation of Nrf2. We found that dietary supplementation of sulforaphane-rich broccoli powder ameliorated kidney disease only in *Gstm1* KO mice. Similarly, in the ARIC study of nearly 11,000 patients, high intake of cruciferous vegetables was associated with lower risks of kidney failure, with stronger effects in those homozygous for the null allele (*GSTM1(0/0)*). Our recently published paper reporting these findings ⁴ was selected for news release based on "its overall excellence in furthering the field of nephrology", and was highlighted in several news outlets, including Science Daily and Reuters Page 1 of 13

Health.

SFN is currently in clinical trials for cancer of the breast, lung, and prostate, as well as autism and schizophrenia, and cardiotoxicity from chemotherapy (Clinicaltrials.gov). However, very few studies have assessed the effect of SFN in kidney disease in pre-clinical experimental models; and, to the best of our knowledge, no clinical study has been performed to assess the effect of SFN in CKD. Our overarching objective is to test the safety, feasibility and efficacy of SFN in delaying CKD progression, and, if so, whether its effect is dependent on *GSTM1* genotype.

Once Phase I is completed and an appropriate dose is established, we will move to our Phase II pilot study in which patients will be randomized to the study drug Avmacol ES and placebo for 6 months. We hope that at the conclusion of the 3-year study, SFN will be demonstrated to be safe and well tolerated, with measurable pharmacodynamic actions. The results would provide a sound rationale for Phase III and a future large multicenter clinical trial to randomize CKD patients to standard care \pm SFN to determine its efficacy in slowing the rate of decline of eGFR in patients with CKD Stages 3-4 and its interaction with GSTM1 genotype. Positive results in our study will also reinforce and establish further mechanistic evidence for future research on the effects of regulation of the Nrf2-GSTM1 pathway on kidney function.

3. ADMINISTRATIVE ORGANIZATION

This is a multi-site collaborative study funded by the National Institutes of Health (NIH). The Nephrology Division at Strong Memorial Hospital (SMH) will conduct the study to enroll patients. Subjects will be recruited from the Kidney Clinic in AC-3, located at SMH, and from Highland Hospital. University of Virginia will serve as a data analysis site (see Section #17). URMC will securely transfer de-identified data to UVA for analysis.

4.1 STUDY INTERVENTIONS

STUDY DRUG: Avmacol Extra Strength capsules

IND # 158689

IND HOLDER: [name]

For Phase I, we will only use Avmacol ES, no placebo, to determine the PK of Avmacol ES in CKD to guide the dose used for Phase II.

Nutramax Laboratories, Consumar Care, Inc., will provide Avmacol ES capsules free of charge in bottles shipped directly to University of Rochester Medical Center (URMC) Clinical Research

Page 2 of 13

Pharmacy Investigational Drug Services (IDS). The IDS will store, monitor, and dispense the drug directly to subjects. Data from the study will be shared with Nutramax.

It should be noted that, compared to control, SFN at "low dose" or 0.5 μM concentration, ex vivo, is able to induce expression of the genes in human peripheral blood mononuclear cells (PBMCs) that encode the enzymes AKR1C1 and NQO1 that play a role in reducing radical species 5. Higher doses of 2 µM and 5 uM of SFN induce higher expression of AKR1C1 and NOO1, as well as HO-1. Other human trials with SFN have reported higher peak plasma concentrations of 1-2 µM ⁶.

GSTM1 genotype will first be determined for the PK analysis to assess whether the genotype influences

drug metabolism. Stratified by GSTM1 group, patients will be assigned randomly to 2 or 4 Avmacol Extra Strength tablets once a day, taken orally with food, as depicted in **Table 1**. The groups are categorized into *GSTM1* null (GSTM1 (0/0) or GSTM1 non-null (GSTM1 (1/1) or (1/0)) genotype based on the dominant model we observed in AASK and ARIC cohorts ^{2,3}.

Table 1: Number of Avmacol Extra Strength Tablets Once a Day				
GSTM1 Genotype	2 Tablets	4 Tablets		
GSTM1 (1/1 or 1/0)	6	6		
GSTM1 (0/0)	6	6		
0071117 (0/0)				

Between 800-900 patients are seen monthly in the URMC Kidney Clinic in AC-3 and Highland Hospital. Among these patients, ~ 60% have CKD Stage 3 or 4, and $\sim 40\%$ of the total patients are African American.

Table 2	Prevalence		
GSTM1 Genotype	Caucasians	African Americans	
GSTM1 (1/1 or 1/0)	50%	73%	
GSTM1 (0/0)	50%	27%	

The null genotype is quite common in human populations, with 50% Caucasians and 27% African Americans being homozygous for the GSTM1 (0/0) allele (see Table 2 for prevalence of GSTM1 genotypes) 7. We saw similar prevalence of genotypes in AASK and ARIC 2-4. Therefore, we do not anticipate difficulty identifying those with null versus non-null genotypes.

Rather than using a dose escalation approach which would take more time, we will be assessing 2 different doses simultaneously in different participants in each group to assess for the degree of variation in PK. We will choose the highest dose that achieves similar $t_{1/2}$ concentration and AUC₀₋₈ of SFN levels as observed in non-CKD patients (1-2 µM) ^{5,6} for our safety and efficacy study in Phase II.

Toxicities and guidelines for adjustments, withdrawals, etc.

In case of any significant side effects, adverse events or unusual changes, dosage will first be halved, and if patient's signs/symptoms do not improve after 3 days, treatment will be stopped. If signs/symptoms are resolved, the treatment will be resumed at the lower dose for 7 days. On Day 7 when the patient comes in for PK study. Otherwise, the study treatment will be stopped. If symptoms recur after resuming the lower dose, Avmacol ES will be discontinued.

Reporting of Side Effects. Participants will be given instructions and contact information to report any side effects, new symptoms or worsening of preexisting symptoms to the research coordinator or their primary nephrologist (who will be made aware of the patient's participation) during work hours. After work hours, including nights and weekends, they will contact [name] who is available 24 hours a day. If [name] is away, the Nephrology physician on call will take the calls for [name], so that 24/7 medical coverage will be available for study participants. Any serious unexpected adverse effects will be immediately reported to the IRB, the DSMB, and the NIH Office of Biotechnology Activities.

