8. STUDY PROCEDURES

Page 5 of 13

SCREENING PROCEDURES:

Avmacol ES has not been tested in patients with CKD. Since sulforaphane (SFN) and its metabolites are cleared by the kidney, to establish a safe dose for our study participants, for Phase I of the study, we will first perform PK analysis in CKD Stage 3B to 4 patients with eGFR between 25 - 45 mL/min/1.73m² who meet the inclusion criteria below. The eGFR result should be within a 2 week window at the time of screening. If eGFR testing was performed longer than 2 weeks, the research coordinator will reach out to the patient's provider to ask for repeat testing.

Our research coordinator will use eRecord EMR to screen patients for enrollment based on inclusion and exclusion criteria listed above in #5. Each week, the research coordinator (RC) will screen subjects scheduled to visit to the Kidney Clinic in the upcoming 1 to 2 weeks for enrollment. The RC will discuss with [name], who will make the final decision for inclusion and exclusion. If eligible and after subject consent is obtained:

A total of 2 in-person study visits will occur for the Phase I study. The first visit (AC3 or Highland Hospital) is expected to last for 1 hour. The second visit will only occur at the Clinical Research Center in Strong Memorial Hospital (SMH) and will take place on day 7 of taking the study drug and is expected to last up to 9-hours to allow biospecimen collections at 5 separate intervals.

RANDOMIZATION:

As noted in Section 4.1 Study Interventions, groups will be stratified by GSTM1 group, patients will be assigned randomly to 2 or 4 Avmacol Extra Strength tablets once a day, taken orally with food, as depicted in Table 1 (below). The groups are categorized into GSTM1 null (GSTM1 (0/0) or GSTM1 nonnull (GSTM1 (1/1) or (1/0)) genotype based on the dominant model we observed in AASK and ARIC cohorts. We do not anticipate difficulty obtaining the different genotype groups, as 75% of Caucasians are either GSTM1 (1/1) or (1/0), and 25 % are GSTM1 (0/0). Approximately 65% of patients in our Kidney Clinic are Caucasians. In African Americans/blacks, approximately 25% are GSTM1 (1/1), 50% are GSTM1 (1/0), and 25 % are GSTM1 (0/0). Approximately 30% of patients in our Kidney Clinic are African Americans. Randomization will be performed by the IDS who will be provided the patients' eGFR and GSTM1 genotypes. Since this is a PK study, the investigators will not be blinded to the randomization.

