9. RISKS TO SUBJECTS

Sulforaphane/Avmacol ES (Study Drug)

There are some potential risks to participants since we are introducing a well-tolerated study drug in other clinical trials but has not been previously tested in CKD patients. We take careful precautions by first establishing an optimal dose of Avmacol ES in CKD patients using reported peak plasma concentrations in trials that were conducted in patients without kidney disease. Based on the multiple clinical trials that have been done with Avmacol or the actual sulforaphane compound in other diseases, we do not anticipate any serious risks. The most common side effects are gastrointestinal, including nausea and dyspepsia, which are ameliorated when taken with food.

Although not reported in any earlier trial, there is the possibility of an allergic reaction to the study drug. This reaction may be mild, such as a skin rash, or more severe symptoms like swelling of the throat, low blood pressure, and shortness of breath. In rare cases, a severe reaction could cause death.

Risks of Blood Draw

The most common risk is pain, bleeding, or bruising at the site of the blood draw. Other risks include redness, and swelling of the vein and infection, and a rare risk of fainting.

Risks of Buccal Swab

The risk is minimal. There is risk of not obtaining adequate sample for DNA extraction.

Risks of Urine Sample

The risk is minimal. There is risk of spilling urine onto clothes.

Risks of Pregnancy: The effect of sulforaphane on the fetus is not known. The patient will be advised to immediately stop taking the drug if pregnancy is suspected and notify the research team.

Risk of Disclosure of Privacy and Confidentiality

Other potential risks involve violations of confidentiality. Procedures for assuring confidentiality are discussed below.

Risks to Social/Emotional Well-Being

We do not anticipate any psychological, social or legal risks beyond those related to participation in a clinical study.

Page 8 of 13

Risks of Ouestionnaires

There are no anticipated risks for subjects to complete the requested questionnaires.

Patients will be informed that declining to participate in this study will not impact their care whatsoever.

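### The Phase II dose rule picks the highest dose on PK similarity alone; in the legible text, no tolerability condition is tied to the choice.

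*Combined protocol and SAP*

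**What the plan says.** Section 4.1 randomises patients, within *GSTM1* group, to 2 or 4 tablets once daily, and states how Phase I will settle the Phase II dose: "We will choose the highest dose that achieves similar" half-life and AUC over 0 to 8 hours to non-CKD patients. Other sections rest on the same basis. Section 8 wants "to establish a safe dose for our study participants" and reaches it through PK analysis. Section 9 describes finding the best dose "using reported peak plasma concentrations in trials that were conducted in patients without kidney disease".

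Tolerability appears elsewhere, for other purposes:

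- For significant side effects in an individual, "dosage will first be halved"; treatment then stops if there is no improvement after 3 days (Section 4.1).
- Patients who leave because side effects did not resolve are replaced (Section 13).
- The DSMB meets at the start and end of Phase I, or sooner for unanticipated events, and reviews unblinded side-effect data. A serious adverse event leads to a meeting on possible suspension (DSMB text before Section 17).
- Adverse events and compliance are summarised descriptively (Section 17).

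On what follows, Section 1 says "Once Phase I is complete, a new study will be submitted for Phase II", and Section 2 says "patients will be randomized to the study drug Avmacol ES and placebo for 6 months".

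**The concern.** The rule defaults to the higher dose and has one test, which is PK. A dose can pass that test while a good share of patients cannot stay on it. Phase I exposes each patient for 7 days and Phase II for 6 months, so a dose that is only just bearable in Phase I could cost adherence and retention in Phase II.

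The expected problems are also of a kind that may not trigger a formal safety review. Section 9 says: "The most common side effects are gastrointestinal, including nausea and dyspepsia". Repeated nausea that leads to halving need not be a serious adverse event, which is the stated trigger for considering suspension.

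Replacement adds a counting problem. If patients who stop are replaced, the group with Day 7 profiles consists increasingly of those who tolerated the dose. A judgement of tolerability made on that group alone would flatter the dose.

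**Working it through.** **Patients per dose.** Section 4.1, Table 1 has 2 genotype groups × 2 doses × 6 = 24, which matches the 24 in Section 4.2. Each dose therefore has 2 × 6 = 12 patients.

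**Reading the rule.** Its inputs are half-life and AUC. Halvings, stops, replacements and adverse events are not among them. Given PK similarity, the probability that poor tolerability rules out a dose under the written rule is 0, whatever the true rate. Halving and stopping act on one patient, the DSMB text names no criterion for choosing between 2 and 4 tablets, and Section 17 is descriptive.

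**What a condition would do.** The documents give no halving or stopping rate, so true rates *p* of 10% to 40% are assumed, with patients independent. With X the number halved or stopped among 12, the chance of passing a limit *c* is P(X ≤ c) = Σ C(12,k) p^k (1−p)^(12−k), summed over k = 0 to c.

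For c = 3 and p = 0.20: 0.0687 + 0.2062 + 0.2835 + 0.2362 = 0.795.

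For c = 3 and p = 0.40: 0.0022 + 0.0174 + 0.0639 + 0.1419 = 0.225.

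| Rule | 10% | 20% | 30% | 40% |
|---|---|---|---|---|
| As written (PK similar) | 100% | 100% | 100% | 100% |
| At most 2 of 12 | 89% | 56% | 25% | 8% |
| At most 3 of 12 | 97% | 79% | 49% | 23% |
| At most 4 of 12 | 100% | 93% | 72% | 44% |

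**Precision.** An observed 3 of 12 has an exact (Clopper-Pearson) 95% interval of 5% to 57%.

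**Denominator.** Suppose 3 patients stop and are replaced, and nobody else is halved or stopped. The number dosed is 12 + 3 = 15. Completers alone show 0 of 12 (95% interval 0% to 26%). Everyone dosed shows 3 of 15, or 20% (4% to 48%).

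**The case against.** The strongest case is that safety already goes to a body that can act at the right time. The DSMB meets at the end of Phase I with side-effect data in hand, and Phase II needs a new submission, so the sentence in Section 4.1 does not by itself put anyone on 4 tablets for 6 months. Matching exposure to non-CKD levels is itself a safeguard. Phase I has no placebo, so attributing side effects to the drug over 7 days is hard. Phase II is placebo-controlled and can test tolerability properly. A limit on 12 patients is crude, and a purely advisory limit would add little to what the DSMB already does.

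Much of this stands. The backstops are real and make it less likely that a poorly tolerated dose goes forward unnoticed. The imprecision is real too. What remains is that neither backstop has a criterion agreed in advance, and the dose that reaches them has been picked by a rule that ignores tolerability. A criterion that applies by default, and that the DSMB may override only with stated reasons, is more than advice.

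There is also a limit on what can be read. The opening of the DSMB text is not available, and the aim in Section 4 is broken by a repeated web address and resumes mid-sentence. A condition could sit in either place, so the claim is confined to the legible text.

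**Conclusion.** The point holds for the legible text: the dose rule has no tolerability condition, and a PK-similar 4-tablet dose passes at any rate of halving or stopping. The rule should be amended before data are seen. The size is illustrative, because the intolerance rates and the limits in the table are assumptions.

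Three stronger readings might be inferred, and the documents do not support them.

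- *That the trial will send a poorly tolerated dose into Phase II unchecked.* The DSMB review and the new submission stand in the way.
- *That adverse events in withdrawn patients are discarded.* Nothing says so. The comparison of 0 of 12 with 3 of 15 shows only why the denominator should be stated.
- *That halved patients distort the PK comparison.* Section 4.1 says that, once symptoms resolve, "the treatment will be resumed at the lower dose for 7 days", and does not say under which dose such a profile is analysed. Section 17 lists the SAP as still to be developed, so this is a minor clarification. If AUC is proportional to dose and patients are grouped by assigned dose, 3 of 12 halved would lower the mean by 0.5 × 3/12 = 12.5%. That is less than one standard error at an assumed CV of 50% (50%/√12 = 14%).

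It is also only an inference that gastrointestinal effects follow tablets swallowed rather than plasma exposure. The conclusion does not depend on it.

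**What to change.** Amend the dose rule in Section 4.1 so that the Phase II dose is the highest one that meets PK similarity and is also acceptably tolerated against a criterion set with the DSMB before data are seen. At most 3 of 12 halved or stopped would be one example. Let the DSMB override it with stated reasons.

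Count the criterion in all patients dosed, by assigned dose, including those halved, stopped or replaced. Replacement takes the number dosed above 12, so write the limit as a proportion (3 of 12 is 25%) or give the allowed count for each number dosed. Report reductions, stops and replacements by assigned dose beside the PK results.

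Separately, a line in the SAP can say how profiles taken at a reduced dose are handled.

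The cost is a sentence or two in Section 4.1 and a short SAP entry. No new data are needed, because symptom questionnaires, intake charts and tablet counts are already collected (Section 8). The downside is imprecision: at most 3 of 12 would fail a dose with a true 20% rate about 21% of the time (1 − 0.795) and pass one with a true 40% rate 23% of the time. That is the reason for the DSMB override.

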13. SUBJECT WITHDRAWALS

- 1. Participants' decision to withdraw from the study for any reason
- 2. Development of side effects that are not resolved by dose reduction
- 3. Failure to adhere to the study protocol
- 4. Relocation resulting in inability to follow up per protocol
- 5. Become pregnant
- 6. New diagnosis of heart failure, cardiovascular event, life threatening infection, or cancer

In the event that a patient drops out the study due to reasons listed above, we will recruit an additional patient to replace.

Once treatment is stopped for any reason, patients will continue to be followed as part of standard of care for CKD. Long-term follow up data will continue to be collected, including their blood pressure, eGFR, and proteinuria.

RETURN OF RESULTS:

Once the study is completed, we will send subjects a summary of the results and what they mean. Subjects will not receive their own individual results.

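### The halve-first toxicity rule has no exception for a severe allergic reaction, so as written it gives the product again to a patient whose reaction has cleared

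*Combined protocol and SAP*

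**What the plan says.** The toxicity paragraph in Section 4.1 (Study Interventions) opens with "In case of any significant side effects, adverse events or unusual changes, dosage will first be halved". It then stops treatment when there is no improvement by 3 days. For the patient who recovers it says "If signs/symptoms are resolved, the treatment will be resumed at the lower dose for 7 days". Otherwise treatment stops, and it is also discontinued if symptoms come back on the lower dose. One sentence in the middle of the paragraph is a fragment.

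Section 9 (Risks to Subjects) foresees an allergic reaction that may be mild or may bring "more severe symptoms like swelling of the throat, low blood pressure, and shortness of breath". It adds: "In rare cases, a severe reaction could cause death". It gives no dosing instruction for that reaction. For pregnancy, the same section does give one: "The patient will be advised to immediately stop taking the drug if pregnancy is suspected and notify the research team".

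Section 13 (Subject Withdrawals) has two relevant items. Item 2 is "Development of side effects that are not resolved by dose reduction". Item 6 is "New diagnosis of heart failure, cardiovascular event, life threatening infection, or cancer". Allergic reaction is not named in the list.

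**The concern.** Halving the dose and waiting suits nausea or dyspepsia, which Section 9 names among the most common side effects. It does not suit a severe allergic reaction, where a small dose may be enough to set off a second episode and recovery from the first is no sign that the product is safe to take again. The Section 4.1 rule treats recovery as the condition for resuming.

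The safety of an individual participant is at stake. The pharmacokinetic result and the choice of the Phase II dose are not affected. The written rule matters because doses before Day 7 are taken at home (Section 8, Visit 1), and because during work hours the first contact for a side effect may be the research coordinator (Section 4.1, Reporting of Side Effects), who would naturally turn to that rule.

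**Working it through.** The plan gives no figure to reproduce, so the check sets the relevant places side by side and follows one patient through the rule.

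**Step 1: scope of the rule.** The Section 4.1 trigger uses *any* and the action uses *first*. No grade, seriousness, causality or allergy qualifier follows.

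**Step 2: does another place override it for a severe allergic reaction?**

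| Place | What it does | Sets a different dosing action for this patient? |
|---|---|---|
| Section 4.1, serious-event sentence | Immediate reporting to oversight bodies | No |
| Section 4.1, round-the-clock physician contact | Allows clinical judgement | Not as a written rule |
| Section 9, allergy text | Describes the risk | No |
| Section 9, pregnancy text | Immediate stop | Pregnancy only |
| Section 13, item 2 | Withdrawal once dose reduction has failed | No; same order as Section 4.1 |
| Section 13, item 6 | Withdrawal for four named kinds of event | Allergy not among them |
| DSMB text before Section 17 | Meeting on whether to suspend the study | No; acts on the study |

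**Step 3: follow a patient through the rule.** A severe allergic reaction is a significant adverse event, so the dose is halved:

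- 2-tablet group: 2 / 2 = 1 tablet
- 4-tablet group: 4 / 2 = 2 tablets

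If the signs clear, the patient resumes at that dose. If symptoms then recur, the product is discontinued. On this path the second reaction is the stopping trigger.

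**Step 4: when does re-exposure arise, and where?** Take the 7-day course in Section 8, with Days 1 to 6 at home and the Day 7 dose at the research center.

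| Reaction after the dose on | Next dose if cleared by the following day | Place |
|---|---|---|
| Days 1 to 5 | Days 2 to 6 | Home |
| Day 6 | Day 7 | Research center |
| Day 7 | None on a 7-day course | Not applicable |

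Re-exposure is therefore possible for a reaction on any of the first 6 days, and the next dose is at home for 5 of them. A slower recovery moves the next dose later, possibly to Day 7 or past the end of the course.

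**Step 5: what cannot be computed.** The number of half doses after a reaction depends on whether dosing continues during the 3-day wait and on what the 7 days at the lower dose mean. The paragraph settles neither, so no total is given. The documents contain no rate for severe allergic reaction, so no probability is given.

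**The case against.** The strongest objection is that this is a claim of absence on incomplete text. The material between Section 15 and the DSMB member descriptions, where Section 16 would begin, was not available for review, and neither were the consent pages or the instructions given to participants. A stop rule may well sit there. That limits the claim to the visible text, but it does not remove the point: the Section 4.1 wording covers every significant event, so it would conflict with such a rule unless it referred to it.

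Second, the literal reading may be strained. The paragraph is headed as guidelines, a 3-day wait fits tolerable symptoms, a physician can be reached at all hours, and a participant may withdraw for any reason. *Resumed* may also imply an unstated pause. This has force: a physician would probably stop the product. But the sentences themselves are directive, and a pause does not prevent re-exposure once the signs clear. The contrast with pregnancy is only supporting evidence, since a suspected pregnancy may cause no symptoms that prompt a call and so needs its own instruction.

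Third, the event is unlikely. Section 9 says earlier trials reported no allergic reaction. That is accepted, and the argument does not rest on frequency.

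A reader might also infer stronger claims that the documents do not support:

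- **That no serious event leads directly to withdrawal.** Section 13 item 6 and the pregnancy item are direct routes.
- **That failure to improve by 3 days is the only stop.** Section 4.1 has two more: a stop otherwise, and discontinuation on recurrence.
- **That every such patient is dosed again.** A reaction to the last dose has no later dose on a 7-day course.

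**Conclusion.** The concern holds in a narrow form. In the visible text, the Section 4.1 rule has no exception for the severe allergic reaction that Section 9 says could be fatal, and Section 13 supplies none. Followed literally, it re-exposes a patient whose reaction clears before the end of dosing.

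This rests on three assumptions: that a severe allergic reaction counts as a significant adverse event under Section 4.1, that the unavailable text contains no overriding rule already linked to that section, and that staff follow the paragraph as written. The likelihood is low and clinical judgement would probably intervene. The change is still worth making, because the written rule points the wrong way for a reaction that the protocol itself describes as possibly fatal, and following it safely would mean departing from it.

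**What to change.** In Section 4.1, limit the halve-first sequence to non-serious, tolerable side effects, such as gastrointestinal ones, and add:

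*Study drug is stopped immediately and not restarted for any suspected severe allergic reaction or any serious adverse event judged possibly related to study drug.*

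The second limb is needed because narrowing halve-first alone would leave other related serious events without a dosing rule for the individual patient. Section 13 item 6 already withdraws its named events and need not be repeated. If the unavailable part of the safety section already holds an equivalent rule, cross-reference it from Section 4.1 instead.

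The cost is a qualifier and one sentence by protocol amendment, with no added visits or samples. The downside is that a rare participant who could have continued is stopped. Section 13 already covers such a loss: "we will recruit an additional patient to replace".
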